### 6.3.1.6 Additional follow-up for QTc prolongation

**Table 6-5 LEE011/placebo dose adjustment and management recommendations for QTcF prolongation (CTC AE v4.03)**

Grade	Dose Modification
For All Grades	
 
1. Check the quality of the ECG and the QT value and repeat if needed
 
2. Perform analysis of serum electrolytes (K+, Ca++, Phos, Mg++). If outside the normal range, interrupt LEE011/placebo administration, correct with supplements or appropriate therapy as soon as possible, and repeat electrolytes until documented as normal.
 
3. Review concomitant medication usage for the potential to inhibit CYP3A4 and/or to prolong the QT interval.
 
4. Check compliance with correct dose and administration of LEE011/placebo.
 

Grade 1* QTc 450-480 ms	Perform steps 1-4 as directed in “For All Grades”. No dose adjustment required.
Grade 2* QTc 481-500 ms	
Interrupt LEE011/placebo. Perform steps 1-4 as directed in “For All Grades.”
 
Perform a repeat ECG within one hour of the first QTcF of ≥ 481 ms. Repeat ECG as clinically indicated until the QTcF returns to < 481ms, restart LEE011/placebo with dose reduced by 1 dose level. Refer to Table 6-2 for dosing schedule.
 
If QTcF ≥ 481 ms recurs, ribociclib should be reduced again by 1 dose level.
 
 
• Repeat ECGs 7 days and 14 days after dose resumption (then as clinically indicated) for any patients who had therapy interrupted due to QTcF ≥ 481 ms
 

Grade	Dose Modification
Grade 3* QTc ≥ 501 ms on at least two separate ECGs	
Interrupt LEE011/placebo. Perform steps 1-4 as directed in “For All Grades.”
 
Perform a repeat ECG within one hour of the first QTcF of ≥501 ms.
 
If QTcF remains ≥ 501 ms, consult with a cardiologist (or qualified specialist) and repeat cardiac monitoring as clinically indicated until the QTcF returns to < 481 ms.
 
 
• If QTcF returns to < 481 ms, LEE011/placebo will be reduced by 1 dose level. Refer to Table 6-2 for dosing schedule.
 
• If QTcF remains ≥ 481 ms after performing steps 1-4 as directed in “For All Grades,” discontinue LEE011/placebo.
 
 
Repeat ECGs 7 days and 14 days after dose resumption (then as clinically indicated) for any patients who had therapy interrupted due to QTcF ≥ 501 ms.
 
If QTcF of ≥ 501 ms recurs, discontinue LEE011/placebo.

Grade 4* [QT/QTc ≥ 501 or > 60 ms change from baseline] and [Torsades de pointes or polymorphic ventricular tachycardia, or signs/symptoms of serious arrhythmia]	
Discontinue LEE011/placebo. Perform steps 1-4 as directed in “For All Grades.”
 
 
• Obtain local cardiologist (or qualified specialist) consultation and repeat cardiac monitoring as indicated until the QTcF returns to <481 ms
 

*All values refer to the average of triplicate measurements	

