## Amendment 5 (06-Aug-2018)

Study CLEE011E2301 was initiated in November 2014 and completed enrollment on 01-Aug-2016 with a total number of 672 randomized patients. The study met its primary endpoint of progression-free survival (PFS) at the time of the primary analysis in October 2017. The study will continue to assess overall survival and to collect safety data.

The purpose of this amendment is to:

- i. Update the dose adjustment and management recommendations for QTcF prolongation. Analyses of preclinical and clinical data with ribociclib have demonstrated that ribociclib prolongs the QT interval in a concentration-dependent manner. Moreover, based on the ribociclib exposure- $\Delta$ QTcF relationship and the clinical experience in studies CLEE011A2301 (MONALEESA-2) and CLEE011E2301 (MONALEESA-7), ribociclib dose reduction is an effective strategy for managing ribociclib therapy in patients experiencing QTcF prolongation. Therefore, in order to reduce the risk of subsequent QTcF prolongation in patients experiencing a QTcF between 481-500 msec, ribociclib dosing should be reduced by 1 dose level with the first occurrence of QTcF  $\geq$  481 msec. As a result, this amendment includes an update to the dosage management guidance for patients who experience QTcF prolongation.
- ii. Update the prohibited concomitant medications based on compilation of drug-drug interaction and co-medication considerations
- iii. As the study has met its primary endpoint, after all patients have gone through 36 months of follow-up from randomization, tumor and other efficacy assessments will be performed as clinically indicated. In order to capture patients PRO data close to the tumor assessment dates, PRO assessment schedule will also follow the efficacy assessment schedule.
- iv. Clarify the timing of collection of patient reported outcomes (PRO) to provide flexibility for sites to collect PRO's at any time during the patient visit but prior to visiting the investigator
- v. Update the withdrawal of consent language to align with the new Global Data Protection Requirements

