### 1.2.1.3 Clinical safety of LEE011

As of 15-Jun-2015, 157 patients have been treated with single agent LEE011 in the first-in-human (FIH) phase I study; 85 patients have been treated in the initial dose escalation part for the 3 week on/1 week off regimen and 47 patients in the dose expansion part of the study; 18 patients were enrolled for the continuous dosing regimen with LEE011 and, 7 patients were enrolled in the liquid formulation cohort.

Patients with advanced solid tumors or lymphomas were treated with increasing doses of LEE011 orally, once daily (qd) for 21 days followed by a 1-week rest (28-day cycle). Doses ranging from 50 mg to 1200 mg were evaluated on this schedule. Treatment has been discontinued in 120 (90%) patients; the primary reasons for treatment discontinuation were: disease progression (106 [80%] patients); AEs (7 [5%] patients); death (2 [1.5%] patients); withdrawal of consent (3 [2%] patient); and loss to follow up (1 [1%] patient).

The most frequently reported AEs ( $\geq 10\%$ ), regardless of grade, causality and LEE011 dose were: nausea (52.3%); fatigue (40.9%); diarrhea (37.1%); vomiting (35.6%); neutropenia (34.1%); anemia (32.6%); decreased appetite (23.5%), thrombocytopenia (23.5%); white blood cell count decrease (22.7%); leukopenia (22%); constipation (21.2%); dyspnea (20.5%); asthenia (19.7%); cough (18.2%); hyperglycemia (17.4%); headache, hypoalbuminemia (16.7% each); ECG QT prolonged (15.9%); abdominal pain, back pain, lymphocyte count decrease, pyrexia (15.2% each); AST increase, blood creatinine increased, dizziness, lymphopenia (14.4% each), peripheral edema (13.6%), neutrophil count decreased (12.9%); ALT increase; pain in extremity (12.1% each) and hypocalcemia (11.4%).

For either continuous or intermittent dosing, the onset of neutropenia (most frequently Grade 2) typically occurs by Day 15, reaching a nadir in the third or fourth week with recovery during the week of drug holiday for the three weeks on/one week off schedule. Some patients require additional time for recovery (7 to 14 days). QT changes become evident in the first cycle by Day 8 and later (once steady state is reached), are associated with the maximum drug levels between 1 to 8 h post-dose, and remain stable or improve in subsequent cycles.

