### 6.1.1 Dosing regimen

LEE011 or LEE011 placebo will be given orally once daily on days 1-21 of each 28 day cycle. Days 22-28 will be a “rest” period from dosing with LEE011 or LEE011 placebo. Tamoxifen, letrozole, and anastrozole will be given orally once daily on a continuous daily schedule (e.g., days 1-28 of each 28 day cycle). Goserelin will be given as an injectable subcutaneous implant on day 1 of every 28 day cycle. There will be no “rest” in the tamoxifen, letrozole, or anastrozole schedule.

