## 7 Visit schedule and assessments

### 7.1 Study flow and visit schedule

Table 7-1a and Table 7-1b list all of the assessments and indicates with an “X”, the visits when they are performed. All data obtained from these assessments must be supported in the patient’s source documentation. The table indicates which assessments produce data to be entered into the database (D) or remain in source documents only (S) (“Category” column). Allowed visit windows are specified as follows:

- There will be no visit window for Cycle 1 Day 1.
- A general +/-3 day window is permitted on assessments to take into account scheduling over public holidays, if not explicitly specified otherwise. Restrict the use of windows before Cycle 3 Day 16 when feasible.

- Radiological assessments must be performed as outlined in Table 7-1a and Table 7-1b. A visit window of +/- 7 days is allowed (The whole body bone scan should be performed within 42 days or 6 weeks prior to randomization).

- Vital signs, physical exam, ECOG performance status, hematology, biochemistry, INR, lipid panel, and urinalysis should be performed within 14 days of randomization.

**Note:** If the physical examination, ECOG performance status, and/or laboratory screening assessments were performed  $\leq 7$  days prior to the first dose of LEE011/placebo, then they do not need to be repeated on Cycle 1 Day 1.

- A +/- 7 day window is permitted on the ECHO/MUGA scans.

- Collection of FSH and/or estradiol (if necessary for determining pre-menopausal status for eligibility) and serum pregnancy test ( $\beta$ -hCG) (unless the patient has had a hysterectomy) must occur within 28 days before starting study treatment.

All other screening assessments must be completed within 28 days before randomization. Every effort should be made to follow the schedule outlined in Table 7-1a.

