#### **7.1.5.1 Discontinuation of study treatment**

Patients **may** voluntarily discontinue from the study treatment for any reason at any time.

If a patient decides to discontinue from the study treatment, the investigator must make reasonable effort (e.g. telephone, e-mail, letter) to determine the primary reason for this decision and record this information in the patient's chart and on the appropriate CRF pages. They may be considered withdrawn if they state an intention to withdraw, fail to return for visits, or become lost to follow-up for any other reason.

The investigator should discontinue study treatment for a given patient if, he/she believes that continuation would be detrimental to the patient's well-being.

Patients may be withdrawn from the study treatment if any of the following occur:

- Adverse Event (including, but not limited to  $QTcF \geq 501$  msec, confirmed at repeated ECG measurements and recurrent after dose adjustment was performed; documented episode of ventricular tachycardia, or ventricular fibrillation)
- Lost to follow-up
- Physician decision
- Progressive Disease

- Protocol deviation
- Study terminated by sponsor
- Technical problems

Patients must be withdrawn from the study treatment if any of the following occur:

- Pregnancy
- Death
- Subject/Guardian decision

In addition to the general withdrawal criteria, the following study specific criteria will also require study treatment discontinuation:

- Adjustments to study treatment that result in discontinuation. Please refer to [Section 6.3](#).
- Use of prohibited medication. Please refer to [Section 6.4.3](#).

Patients who discontinue study treatment should NOT be considered withdrawn from the study. They should return for the assessments indicated in [Section 7.1](#). If they fail to return for these assessments for unknown reasons, reasonable effort (e.g. telephone, email, letter) should be made to contact them as specified in [Section 7.1.5](#).

Patients who discontinue study treatment should undergo an End of Treatment (EOT) visit followed by a 30 day safety follow-up.

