**Table 7-5 Central ECG collection plan**

Cycle	Patients	Day	Time	ECG Type
Screening	All	-14 to -1	Anytime	Triplicate 12 Lead
1	All	Day 1	Pre-dose 	Triplicate 12 Lead
	All	Day 15 	Pre-dose 	Triplicate 12 Lead
	All		2 h post-dose (± 15 min)	Triplicate 12 Lead
	All		4 h post-dose (± 15 min)	Triplicate 12 Lead
2	All	Day 1	Pre-dose 	Triplicate 12 Lead
3	All	Day 1	Pre-dose 	Triplicate 12 Lead

Cycle	Patients	Day	Time	ECG Type
3	All	Day 15 	Pre-dose 	Triplicate 12 Lead
	All		2 h post-dose (± 15 min)	Triplicate 12 Lead
4	All	Day 1	Pre-dose 	Triplicate 12 Lead
5	All	Day 1	Pre-dose 	Triplicate 12 Lead
6	All	Day 1	Pre-dose 	Triplicate 12 Lead
			2h post-dose (± 15 min)	Triplicate 12 Lead
All other cycles	As clinically indicated		Anytime	Triplicate 12 Lead
EOT			Anytime	Triplicate 12 Lead
Unscheduled ECG			Anytime	Triplicate 12 Lead
 The exact date and time of dosing must be recorded on the appropriate eCRF.  ECG assessments are to be done prior [REDACTED] (if applicable)				

ECG Schedule of assessments for cross over patients:

Patients	Cross Over Cycle	Day / time	ECG type
All	1	1/Pre-dose	Triplicate 12 Lead
All	1	15/anytime	Triplicate 12 Lead
All	2	1/ anytime	Triplicate 12 Lead
All	All other cycles as clinically indicated		Triplicate 12 Lead

In order for an accurate evaluation of baseline QTcF, a total of three 12-lead ECGs will be performed pre-dose on Cycle 1 Day 1.

**Note:** In order to ensure ECG evaluation is received from the central laboratory for eligibility assessment, it is advisable to perform the ECG at least 24 hours prior the scheduled randomization date.

If any of the triplicate readings include an abnormal ECG or an average QTcF value of  $\geq 481$  is obtained at any time after randomization, study treatment must be interrupted, repeat ECG (triplicate) and follow management guidelines detailed in [Table 6-5](#).

An unscheduled ECG may be repeated at the discretion of the investigator at any time during the study and as clinically indicated. Unscheduled ECGs with clinically significant findings should be collected in triplicate. Local cardiologist ECG assessment may be performed at any time during the study at the discretion of the investigator.

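### The two ECGs that check a reduced LEE011 dose after QTcF prolongation are set by calendar day; for resumption on cycle Day 15 neither is taken near peak exposure, and no post-dose time is required on any day

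*Protocol*

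**What the plan says.** In protocol Section 6.3.1.6, the Grade 2 and Grade 3 rows of Table 6-5 restart LEE011 one dose level lower and then require: "Repeat ECGs 7 days and 14 days after dose resumption (then as clinically indicated". Neither row names a cycle day or a time after dose. A recurrence at 501 ms or more in the Grade 3 row means discontinuation. Section 7.1.5.1 likewise lists QTcF of that size, "confirmed at repeated ECG measurements and recurrent after dose adjustment was performed", among the adverse events for withdrawal from treatment.

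Section 6.1.1 sets the dosing: "LEE011 or LEE011 placebo will be given orally once daily on days 1-21 of each 28 day cycle". Days 22-28 are off drug. Section 1.2.1.3 says that QT changes become evident once steady state is reached and "are associated with the maximum drug levels between 1 to 8 h post-dose".

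Elsewhere the protocol does time ECGs to the dose. Several rows of Table 7-5 specify "2 h post-dose (± 15 min", and some also 4 h. After Cycle 6 the schedule becomes "All other cycles As clinically indicated". For crossover patients the last scheduled on-treatment ECG is crossover Cycle 2 Day 1.

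**The concern.** The repeat ECGs are there to show whether QTcF is safe on the lower dose. By the protocol's own account the effect follows peak drug level at steady state. A calendar rule combined with a week off drug can put the first ECG in the rest week and the second only one to three doses into the next cycle. Both may then look reassuring because exposure is low, not because the dose is tolerated. At stake is a recurrence that would require a further reduction or, at 501 ms, discontinuation.

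The case is foreseeable. Table 7-5 and the crossover schedule both place an ECG on Day 15 of the first cycle, so an event found there may lead to resumption on that day or shortly after. For a crossover patient the only remaining scheduled ECG would be Cycle 2 Day 1, straight after the rest week.

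**Working it through.** **Calendar.** I assume the 28-day cycle is not reset by an interruption. No section says this outright. It is supported by Section 6.1.1.1 (missed doses are not made up), by goserelin being tied to Day 1 of each cycle, and by Section 6.3.1.4, which leaves the visit schedule unchanged after inadvertent rest-day dosing. Resumption on Day 15, 16 or 17 then puts the 7-day ECG on Day 22, 23 or 24 and the 14-day ECG on next-cycle Day 1, 2 or 3.

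**Half-life.** Section 1.2.1.5 gives accumulation ratios R of 1.35 to 3.11 and effective half-lives of 12.3 to 42.9 h. The formula h = 24 ln2 / ln(R/(R-1)) gives 12.3 h for R = 1.35 and 42.9 h for R = 3.11, which reproduces the stated range. Table 1-3 (600 mg without letrozole, geometric means) gives two values inside it:
- AUC: R = 24500/10100 = 2.426, h = 31.3 h
- Cmax: R = 1790/1030 = 1.738, h = 19.4 h

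**Exposure on the ECG day.** I add up once-daily doses. With q = 2^(-24/h), the level on day t relative to steady-state peak is (1-q) times the sum of q^(t-d) over doses given on days d up to t. An ECG on a dosing day is taken just after the dose.

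Example, resumption on Day 15 at 31.3 h (q = 0.588):
- Day 22, after seven doses: q(1-q^7) = 0.588 x 0.976 = 57.4%.
- Next-cycle Day 1: (1-q) plus the remainder, q^8(1-q^7) = 0.412 + 0.014 = 42.6%.

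Better of the two ECGs under Table 6-5, as % of steady-state peak:

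| Resumption day | 31.3 h | 19.4 h | 12.3 h | 42.9 h |
|---|---|---|---|---|
| 15 | 57.4 | 57.6 | 74.1 | 63.4 |
| 16 | 66.3 | 82.0 | 93.3 | 56.7 |
| 17 | 80.2 | 92.4 | 98.3 | 70.5 |
| 18 | 88.3 | 96.8 | 99.6 | 79.9 |

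At 31.3 h, Days 8-14 give 98.6% (1-q^8), Days 1-7 nearly 100%, and Days 19-21 give 93-98%.

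**Effect of post-dose timing.** If on-drug ECGs are taken before the dose, the best value at 31.3 h falls to 57-59% for Days 1-14 and to 57%, 33% and 39% for Days 15, 16 and 17.

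**First ECG moved to Day 21, post-dose:**

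| Resumption day | 31.3 h | 19.4 h | 12.3 h | 42.9 h |
|---|---|---|---|---|
| 15 | 97.6 | 99.8 | 100.0 | 93.4 |
| 16 | 95.9 | 99.4 | 100.0 | 90.2 |
| 17 | 93.0 | 98.6 | 99.9 | 85.6 |
| 18 | 88.1 | 96.8 | 99.6 | 78.8 |

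Moving the ECG helps at every half-life for Days 15-17. It gains nothing for Day 18 (88.1% against 88.3%; 78.8% against 79.9%).

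**Consequence in ms.** Assume that the QTcF rise is proportional to exposure and to dose, and that baseline B is 420 ms (my assumption) or 450 ms (the eligibility limit). On 400 mg, QTcF = B + (Q600 - B) x 2/3, where Q600 is QTcF on 600 mg.
- Q600 = 500 ms gives 473-483 ms.
- Reaching 481 ms on 400 mg needs Q600 of about 497-512 ms.
- Reaching 501 ms on 400 mg needs Q600 of about 527-542 ms.

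**The case against.** Much of the case on the other side stands.

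- **Choice of half-life.** Section 1.2.1.3 ties QT to maximum levels, so the Cmax ratio has at least as good a claim as the AUC ratio. On Cmax, Days 16 and 17 reach 82% and 92%. A reader might infer from the 31.3 h column that all three days are badly covered. The documents do not support that: 31.3 h is not printed anywhere, it comes from preliminary 600 mg data, and only Day 15 is low at every half-life.
- **Small harm.** On the linear model a Grade 2 patient can hardly recur at 400 mg. Section 1.2.1.5 says exposure rises slightly more than in proportion to dose, so the reduction probably does more than the model credits. Amendment 5 states that "ribociclib dose reduction is an effective strategy for managing ribociclib therapy in patients experiencing QTcF prolongation", and Section 1.2.1.3 says that QT changes hold steady or ease in later cycles. It would be wrong to infer that the plan lets dangerous recurrences pass: no missed-event rate can be derived.
- **Few patients.** Amendment 7 counts 79 ribociclib-arm patients and 8 crossovers on treatment on 08-Jan-2020. A further 35 - 8 = 27 placebo-arm patients could still elect to cross over.
- **Existing latitude.** Clinical judgment, unscheduled ECGs and the visit window all permit a better day. But the window reads "A general +/-3 day window is permitted on assessments to take into account scheduling over public holidays", and the same section asks sites to restrict its use before Cycle 3 Day 16. These provisions allow a well-timed ECG without directing anyone to take one.
- **Arbitrary cut-off.** This does not stand. Day 17 gains from a Day 21 ECG at every half-life and Day 18 does not.

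**Conclusion.** The point holds as a narrow gap of low consequence. For resumption on Day 15, neither mandated ECG exceeds about 57-74% of steady-state peak. For Days 16 and 17 the better ECG lies between 57% and 93% and between 71% and 98%, depending on half-life. For all other days one ECG is adequate at 31.3 h (80% for Day 18 at 42.9 h), provided it is taken after the dose. Table 6-5 does not require that, and the omission affects more resumption days than the rest-week clash does.

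This rests on an unreset 28-day calendar, simple superposition of doses, and half-lives derived from 600 mg data although patients resume at a lower dose. The documents do not say how often patients resume on Days 15-17. The gap matters mainly after Grade 3 events and for crossover patients, who have no scheduled on-treatment ECG after crossover Cycle 2 Day 1. No efficacy endpoint or inference is affected.

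**What to change.** Add to the Grade 2 and Grade 3 rows of Table 6-5:

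*A repeat ECG that falls on a LEE011 dosing day is taken 1-8 h post-dose. If dosing resumes on cycle Days 15-17, take the first repeat ECG on Day 21 (post-dose) instead of at 7 days; keep the second ECG at 14 days.*

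Leave the days unchanged for every other resumption day. State the Day 21 rule as an explicit exception to the Section 7.1 instruction to restrict visit windows before Cycle 3 Day 16.

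Cost: two table rows in a protocol amendment, with the approvals that Section 12.1 requires. No ECG is added. For resumption on Days 15, 16 and 17 the first ECG comes 1, 2 and 3 days earlier, after 7, 6 and 5 doses. On-drug repeat ECGs need post-dose timing, which sites already know from Table 7-5.

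### Table 6-5 does not say which row governs an unconfirmed QTcF of 501 ms or more, and in two situations its rows lead to different actions: permanent stop, or restart at a lower dose.

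*Protocol*

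**What the plan says.** Table 6-5 (Protocol Section 6.3.1.6) attaches an action to each grade of QTcF prolongation. Its footnote makes every value the average of a triplicate, so one triplicate counts as one value.

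- **Grade 2 row.** The label covers 481–500 ms. The instructions are to interrupt, repeat the ECG within an hour of the first value of 481 ms or more, and continue ECGs until QTcF is below 481 ms. Then the site is to "restart LEE011/placebo with dose reduced by 1 dose level". If 481 ms or more recurs, the dose drops by one further level.
- **Grade 3 row.** The label is "QTc ≥ 501 ms on at least two separate ECGs". The instructions are to interrupt and "Perform a repeat ECG within one hour of the first QTcF of ≥501 ms". Next comes a confirmation branch, "If QTcF remains ≥ 501 ms, consult with a cardiologist (or qualified specialist", with monitoring until QTcF is below 481 ms. Two bullets follow. If QTcF falls below 481 ms, "LEE011/placebo will be reduced by 1 dose level". The other bullet begins "If QTcF remains ≥ 481 ms after performing steps 1-4 as directed in" the all-grades box, and ends in discontinuation. A final line reads "If QTcF of ≥ 501 ms recurs, discontinue LEE011/placebo".
- **Section 6.3.1.4.** Physician judgment guides management in general, but discontinuations required by the dose-modification tables, and events listed in Section 7.1.5.1, are mandatory.
- **Section 7.1.5.1.** QTcF of 501 ms or more appears among the reasons for which a patient may be withdrawn, qualified as "confirmed at repeated ECG measurements and recurrent after dose adjustment was performed".
- **Section 7.2.2.7.1.** Any average QTcF of 481 ms or more after randomization requires interruption and a repeat triplicate, and the site is then referred to Table 6-5.

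**The concern.** The Grade 3 label and the Grade 3 instructions use different entry criteria: two separate ECGs in one, the first value in the other. A first value of 501 ms or more that the repeat does not confirm lies above the Grade 2 label and fails the Grade 3 label, yet the instructions of both rows can be entered with it. Where those instructions end differently, two sites with the same pair of ECGs can reach opposite decisions on permanent discontinuation, each with support in the text.

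The table matters because QT prolongation is described as an important identified risk (Protocol Section 1.4.1.1). Section 6.1 relies on Table 6-5 for patients remaining on LEE011 plus tamoxifen, and Section 7.1 sends crossover patients to the same table. Since Amendment 6 the ECGs are read locally. There is also a reporting consequence: the SAP for the final report (Section 3.7.1.4) tabulates adverse events leading to study drug discontinuation separately from those leading to reduction, so the row a site follows decides where the event is counted.

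**Working it through.** The plan states no figure to reproduce and no arithmetic is involved. The check is to take a triplicate average of 501 ms or more, let the repeat fall in each band of the table, and read off the action under every line that could apply.

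| Situation | Grade 3 row | Grade 2 row | Other sections | Same action? |
|---|---|---|---|---|
| First episode, repeat ≥501 ms | Label met; the row applies | Label exceeded | None in conflict | Not in dispute |
| First episode, repeat 481–500 ms (for example 505 then 490 ms) | Label not met. The discontinuation bullet, if it stands alone, gives a permanent stop | Hold until <481 ms, then restart one level lower | 6.3.1.4: a discontinuation required by the table is mandatory | **No** |
| First episode, repeat <481 ms | Restart one level lower | Restart one level lower | None in conflict | Yes |
| Later value ≥501 ms, not confirmed | Recurrence line gives a permanent stop, with no mention of confirmation | Recurrence line (≥481 ms) gives one further reduction | 7.1.5.1: confirmed and recurrent, and withdrawal is permitted; 6.3.1.4: events listed in 7.1.5.1 must be discontinued | **No** |

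**Second situation, 505 then 490 ms.** The value of 490 ms has not fallen below 481 ms. The bullet beginning "If QTcF remains ≥ 481 ms after performing steps 1-4 as directed in" is therefore satisfied on its words once the all-grades steps are done, and it gives no interval over which QTcF must remain raised. The repeat also lies within the Grade 2 label, and the Grade 2 instructions are triggered by a first value of 481 ms or more with no upper bound, so 505 ms enters them too. One route ends in permanent discontinuation and the other in re-dosing.

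**Fourth situation, a later unconfirmed value.** A value of 505 ms satisfies "If QTcF of ≥ 501 ms recurs, discontinue LEE011/placebo" and also satisfies the Grade 2 recurrence wording. Section 7.1.5.1 adds a confirmation requirement that the Grade 3 recurrence line lacks. The force of the rule differs as well: 7.1.5.1 lists the event as one for which withdrawal is allowed, while 6.3.1.4 says that events listed there require discontinuation.

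**Does another section settle it?** Section 7.2.2.7.1 requires interruption at 481 ms or more and then refers back to Table 6-5. It supports interrupting on the first value but is silent on what follows. Section 6.3.1.4 makes a table discontinuation binding but does not say which row governs. No other section names a row for an unconfirmed value of 501 ms or more.

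**The case against.** The strongest reply concerns layout. The discontinuation bullet sits beneath "If QTcF remains ≥ 501 ms, consult with a cardiologist (or qualified specialist", so both bullets can be read as outcomes of the confirmed branch. The one-hour repeat is then simply the step that establishes whether the label is met. On that reading 505 then 490 ms never becomes Grade 3, the Grade 2 row takes over, and the first divergence disappears. The reading is plausible, but the table does not state it, and the row is written to be entered at the first value. Because 6.3.1.4 makes table discontinuations mandatory, the point should not rest on indentation.

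A second reply is that 7.1.5.1 gives QTcF only as an example under permissive withdrawal and defers to Section 6.3 for discontinuations arising from dose adjustment. Its wording also fits a confirmed Grade 3 event that recurs. That is fair, and it weakens 7.1.5.1 as an independent source of conflict. It does not supply the missing confirmation in the table's own recurrence line, or reconcile the permissive wording with 6.3.1.4.

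A reader might infer more than the text supports:

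- **That every unconfirmed value of 501 ms or more is left without a row, or splits the outcome.** The Grade 2 instructions capture such a value, and in a first episode with a repeat below 481 ms both rows restart one level lower.
- **That interrupting on the first value is itself a contradiction.** Section 7.2.2.7.1 requires that interruption.
- **That the 5.4% at 600 mg with QTcF of 500 ms or more (Section 1.2.1.3) gives the number affected.** That figure comes from a single-agent phase I study, uses a different cut-off, and does not say whether readings were confirmed. In the phase III letrozole combination trial, 3.3% exceeded 480 ms (Section 1.4.1.1), again with no count of unconfirmed values.

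**Conclusion.** Wrong as written, as an internal inconsistency rather than a design choice. The Grade 3 label and instructions of Table 6-5 use different entry criteria, and no passage assigns a row to an unconfirmed value of 501 ms or more. The permanent-stop and lower-dose routes diverge in two situations only: a first value of 501 ms or more with a repeat of 481–500 ms, and a later unconfirmed value of 501 ms or more. The first depends on not confining the discontinuation bullet to the confirmed branch. The second arises from the two recurrence lines themselves and does not need that assumption.

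The documents do not allow the frequency to be estimated. They do bound the exposed group at one date: on 8 January 2020 (Amendment 7 summary), 79 patients on the ribociclib arm and 8 crossed-over patients were on study treatment, so up to 79 + 8 = 87 were on LEE011. That is the number to whom the rule could apply, not the number affected by the ambiguity. The conclusion is about the text and takes no view on which clinical action is right.

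**What to change.** Reconcile five places: the Grade 3 label, the Grade 3 instructions including the recurrence line, the Grade 2 row, Section 6.3.1.4 and Section 7.1.5.1. The revised text should:

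- use one entry criterion, stating whether a single or a confirmed triplicate average counts;
- state whether the discontinuation bullet belongs only to the confirmed branch;
- name one row for an unconfirmed value of 501 ms or more, both at first occurrence with a repeat of 481–500 ms and at recurrence;
- give the QTcF event in 7.1.5.1 the same force (permitted or required) as in 6.3.1.4.

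Which action applies in each case is for the sponsor's clinical team. The cost is a wording clarification in the table and the two sections, with no new assessment.
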